4. SUBJECT DISPOSITION

4.1. Subject Enrollment and Disposition

Subject enrollment summaries were performed as part of the Week 48 analysis and will not be repeated in the final analysis. The randomization schedule used for the study will be provided as an appendix to the CSR.

The summary of subject disposition will be provided by treatment group and overall for all screened subjects. This summary will include the number of subjects screened, screen failure subjects who were not randomized, subjects who met all eligibility criteria and were not randomized, subjects in the Randomized Analysis Set, subjects randomized but never treated, subjects in the Safety Analysis Set, subjects in the FAS, subjects in the Open-Label Safety Analysis Set, subjects in the TFFU Safety Analysis Set, and subjects in the TFFU FAS.

In addition, the number and percentage of the subjects in the following categories will be summarized using the Safety Analysis Set:

Double-blind Study Drug Completion

- Prematurely discontinued double-blind study treatment (with summary of reasons for discontinuing treatment)
- Completed double-blind study treatment

Open-label Study Drug Completion

- Willing to enter open-label phase
- Prematurely discontinued open-label study treatment (with summary of reasons for discontinuing treatment)
- Completed open-label study treatment

Study Completion

- Entered 24-week treatment-free follow-up period
- Prematurely discontinued study (with summary of reasons for discontinuing study)
- Completed protocol-planned duration of the study
- Started another HBV therapy

No inferential statistics will be generated. A data listing of reasons for premature study drug/study discontinuation will be provided.

4.2. Extent of Study Drug Exposure and Adherence

Exposure data described below will be summarized for double-blind phase and open-label phase separately.

4.2.1. Duration of Exposure to Blinded Study Drug

Duration of exposure to blinded study drug will be defined as (last dose date of blinded study drug first dose date of blinded study drug + 1), regardless of temporary interruptions in study drug administration, and will be expressed in weeks (recorded to 1 decimal place, eg, 4.5 weeks).

Duration of exposure to blinded study drug will be summarized using descriptive statistics (sample size, mean, SD, median, Q1, Q3, minimum, and maximum) and as the number and percentage of subjects exposed for specified periods, eg, \geq 4 weeks (28 days), \geq 8 weeks (56 days), \geq 12 weeks (84 days), \geq 24 weeks (168 days), \geq 36 weeks (252 days), \geq 48 weeks (336 days).

Summaries will be provided by treatment group for subjects in the Safety Analysis Set. No inferential statistics will be provided.

4.2.2. Adherence with Blinded Study Drug Regimen

Study drug regimen adherence will be computed based on tablet counts for the active drug only (eg, adherence in TAF group only includes TAF and not placebo for TDF). The numbers of tablets of study drug dispensed and returned are captured on study drug accountability forms.

Adherence (%) of study drug regimen will be calculated as follows:

Adherence (%)
$$100 \times \frac{\text{Number of tablets taken}}{\text{Number of tablets prescribed}}$$

$$100 \times \frac{\sum \text{No. of tablets taken at each dispensing period [1]}}{(\sum \text{No. of tablets prescribed at each dispensing period [2])} + 1}$$

- [1] Number of tablets taken at a distinct dispensing period for a study drug is calculated as the minimum of (a) the daily number of tablets prescribed for the study drug multiplied by (the duration of treatment +1 day) at the dispensing period of the same dispensing date, and (b) the number of tablets taken for the study drug (number of tablets dispensed minus the number of tablets returned). Total number of tablets taken is determined by summing the number of tablets taken from all evaluable dispensing periods.
- [2] Number of tablets prescribed at a distinct dispensing period for a study drug is calculated as the daily number of tablets prescribed for the study drug multiplied by **the duration of treatment** at the dispensing period of the same dispensing date. Total number of tablets prescribed is determined by summing the number of tablets prescribed from all evaluable dispensing periods.

The duration of treatment at a dispensing period for a study drug is calculated as the minimum of (a) the last returned date of the same dispensing period for the study drug, (b) date of premature discontinuation of the study drug, and (c) next dispensing date of the study drug, minus dispensing date of the study drug.

The next dispensing date is the following dispensing date of the study drug regardless of the bottle return date.

For a record where the number of tablets returned was missing (with "Yes" answered for "Was bottle returned?" question), it is assumed the number of tablets returned was 0. If the number of tablets dispensed was missing or any study drug bottle was not returned or the bottle return status was unknown for the same dispensing date, then all records for the same dispensing date for that study drug will be excluded from both denominator and numerator calculation.

Adherence up to the Week 48 visit for blinded study drug will be calculated using all data from the entire dosing period up to the date of permanent discontinuation of the blinded study drug for subjects who prematurely discontinued blinded study drug, or completed blinded study drug.

The number and percentage of subjects who return at least 1 bottle and have calculable adherence during the study, descriptive statistics for adherence up to Week 48 visit for the blinded study drug regimen (sample size, mean, SD, median, Q1, Q3, minimum, and maximum) along with the number and percentage of subjects belonging to adherence categories (eg, < 80%, $\ge 80\%$ to < 90%, $\ge 90\%$ to < 95%, $\ge 95\%$) will be provided by treatment group for the Safety Analysis Set. No inferential statistics will be provided.

4.2.3. Duration of Exposure to Open-Label Study Drug

Duration of exposure to open-label study drug will be defined as (last dose date of open-label study drug first dose date of open-label study drug + 1), regardless of temporary interruptions in study drug administration, and will be expressed in weeks (recorded to 1 decimal place, eg, 4.5 weeks).

Duration of exposure to open-label study drug will be summarized using descriptive statistics (sample size, mean, SD, median, Q1, Q3, minimum, and maximum) and as the number and percentage of subjects exposed for specified periods, eg, \geq 12 weeks (84 days), \geq 24 weeks (168 days), \geq 36 weeks (252 days), \geq 48 weeks (336 days).

Summaries will be provided by treatment group for subjects in the Open-Label Safety Analysis Set. No inferential statistics will be provided.

4.2.4. Adherence with Open-Label Study Drug Regimen

Study drug regimen adherence will be computed based on tablet counts for open-label TAF. The numbers of tablets of study drug dispensed and returned are captured on study drug accountability forms.

Adherence (%) of study drug regimen will be calculated as follows:

Adherence (%)
$$100 \times \frac{\text{Number of tablets taken}}{\text{Number of tablets prescribed}}$$

$$100 \times \frac{\sum \text{No. of tablets taken at each dispensing period [1]}}{(\sum \text{No. of tablets prescribed at each dispensing period [2])} + 1$$

- [1] Number of tablets taken at a distinct dispensing period for a study drug is calculated as the minimum of (a) the daily number of tablets prescribed for the study drug multiplied by (the duration of treatment +1 day) at the dispensing period of the same dispensing date, and (b) the number of tablets taken for the study drug (number of tablets dispensed minus the number of tablets returned). Total number of tablets taken is determined by summing the number of tablets taken from all evaluable dispensing periods.
- [2] Number of tablets prescribed at a distinct dispensing period for a study drug is calculated as the daily number of tablets prescribed for the study drug multiplied by **the duration of treatment** at the dispensing period of the same dispensing date. Total number of tablets prescribed is determined by summing the number of tablets prescribed from all evaluable dispensing periods.

The duration of treatment at a dispensing period for a study drug is calculated as the minimum of (a) the last returned date of the same dispensing period for the study drug, (b) date of premature discontinuation of the study drug, and (c) **next dispensing date** of the study drug, minus dispensing date of the study drug.

The next dispensing date is the following dispensing date of the study drug regardless of the bottle return date.

For a record where the number of tablets returned was missing (with "Yes" answered for "Was bottle returned?" question), it is assumed the number of tablets returned was 0. If the number of tablets dispensed was missing or any study drug bottle was not returned or the bottle return status was unknown for the same dispensing date, then all records for the same dispensing date for that study drug will be excluded from both denominator and numerator calculation.

Adherence for open-label study drug will be calculated using all data from the entire open-label dosing period up to the date of permanent discontinuation of the open-label study drug for subjects who prematurely discontinued open-label study drug, or completed open-label study drug.

The number and percentage of subjects who return at least 1 bottle and have calculable adherence during the study, descriptive statistics for adherence for the open-label study drug regimen (sample size, mean, SD, median, Q1, Q3, minimum, and maximum) along with the number and percentage of subjects belonging to adherence categories (eg, < 80%, $\ge 80\%$ to < 90%, $\ge 90\%$ to < 95%, $\ge 95\%$) will be provided by treatment group for the Safety Analysis Set. No inferential statistics will be provided.

4.3. Protocol Deviations

A by-subject listing will be provided for those subjects in the Randomized Analysis Set who did not meet at least 1 eligibility (inclusion or exclusion) criterion. The listing will present the eligibility criterion (or criteria if more than 1 deviation) that subjects did not meet and related comments, if collected.

Protocol deviations occurring after subjects entered the study are documented during routine monitoring. The number and percentage of subjects with important protocol deviations by deviation reason (eg, nonadherence to study drug, violation of select inclusion/exclusion criteria) will be summarized by treatment group for the Randomized Analysis Set. A by-subject listing will be provided for subjects with important protocol deviations.

A separate by-subject listing of subjects who received the incorrect study drug will also be provided.

5. BASELINE CHARACTERISTICS

5.1. Demographics and Baseline Characteristics

Subject demographic data (eg, age, sex, race, and ethnicity) and baseline characteristics (eg, body weight, height, body mass index [BMI], and Vitamin D) will be summarized by treatment group and overall using descriptive statistics (sample size, mean, SD, median, Q1, Q3, minimum, and maximum) for continuous data and by the number and percentage of subjects for categorical data. Age is calculated as age in years at the first dose of study drug. The summaries of demographic data and baseline subject characteristics will be provided for the Open-Label Safety Analysis Set.

In addition, the following baseline characteristics and medical history will be summarized:

- Age group (< 50 years, ≥ 50 years and further split into ≥ 50 to < 60 years and > 60 years)
- Region (Asia, Europe or North America)
- BMI categories (< 18.5 kg/m^2 [underweight], $\geq 18.5 25.0 \text{ kg/m}^2$ [normal], $\geq 25.0 30.0 \text{ kg/m}^2$ [overweight], and $\geq 30.0 \text{ kg/m}^2$ [obese])
- HBV DNA categories ($< 20 \text{ IU/mL}, 20 \text{ to} < 69 \text{ IU/mL}, \ge 69 \text{ IU/mL}$)
- HBsAg (log₁₀ IU/mL)
- ALT (U/L)
- ALT level based on central laboratory normal range (\leq ULN, > ULN 5 \times ULN, > 5 \times ULN)
- ALT level based on 2018 AASLD normal range with the ULN as 25 U/L for females and 35 U/L for males (\leq ULN, > ULN 5 \times ULN, > 5 \times ULN)
- HBeAg and HBeAb status (HBeAg positive, HBeAg negative/HBeAb negative, HBeAg negative/HBeAb positive)
- Years positive for HBV
- Cirrhosis history (yes, no, indeterminate/unknown)
- FibroTest score
- Fibrosis stage by FibroTest score (0 0.48, 0.49 0.74, 0.75 1)
- Estimated GFR by CG, CKD-EPI creatinine, and CKD-EPI Cystatin C methods
- Proteinuria by urinalysis (dipstick) (Grade 0, Grade 1, Grade 2, Grade 3)

- Clinical BMD status for hip and spine (normal, osteopenia, osteoporosis)
- Hip fracture and major osteoporotic fracture probabilities estimated using FRAX® (see Section 7.3.4)
- Previous experience with treatment other than TDF (yes, no)
- Previous interferon experience (yes, no)
- Medical history: diabetes mellitus (yes, no), hypertension (yes, no), cardiovascular disease (yes, no), and hyperlipidemia (yes, no)

Diabetes mellitus, hypertension, cardiovascular disease, and hyperlipidemia above are determined by medical history, adverse events, and concomitant medication data, which will be reviewed by the Gilead medical monitor before to data finalization for the final analysis.

5.2. Medical History

Medical history will be collected at screening for disease-specific and general conditions (ie, conditions not specific to the disease being studied). A listing of medical history data will be provided using the Randomized Analysis Set.

6. EFFICACY ANALYSES

For the final analysis, efficacy data will be summarized for (1) subjects in the FAS from baseline up to Week 96 and statistical comparisons will be performed, (2) subjects in the Open-Label FAS from open-label baseline up to Week 96 and no statistical comparisons will be performed, and (3) subjects in the TFFU FAS from TFFU baseline to the end of the study and no statistical comparisons will be performed. All efficacy data, including data collected during the 24-week TFFU period, will be listed.

6.1. Primary Efficacy Endpoint

6.1.1. Definition of the Primary Efficacy Endpoint

The primary efficacy endpoint is the proportion of subjects with HBV DNA \geq 20 IU/mL (as determined by the modified US FDA-defined snapshot algorithm) at Week 48. The primary efficacy endpoint was analyzed in the Week 48 analysis and will not be re-analyzed in the final analysis. Details are provided in the Week 48 SAP.

6.2. Secondary Efficacy Endpoints

6.2.1. Definition of Secondary Efficacy Endpoints

The secondary efficacy endpoints are:

- The proportion of subjects with HBV DNA ≥ 20 IU/mL (as determined by the modified US FDA-defined snapshot algorithm) at Week 96
- The proportion of subjects with HBV DNA < 20 IU/mL and target detected/not detected (ie, < LLOD) at Weeks 48 and 96
- The proportion of subjects with HBeAg loss and proportion with seroconversion to anti-HBe at Weeks 48 and 96
- The proportion of subjects with HBsAg loss and proportion with seroconversion to anti-HBs at Weeks 48 and 96
- The proportion of subjects with normal ALT and proportion with normalized ALT (by central laboratory and AASLD criteria) at Weeks 48 and 96
- The change from baseline in fibrosis as assessed by FibroTest at Weeks 48 and 96

For the final analysis, the following definitions will be used:

- HBsAg loss is defined as HBsAg test result changes from HBsAg positive at baseline to HBsAg negative at a postbaseline visit with baseline HBsAb negative or missing.
- HBeAg loss is defined as HBeAg test result changes from HBeAg positive at baseline to HBeAg negative at a postbaseline visit with baseline HBeAb negative or missing.
- HBsAg seroconversion is defined as HBsAg loss and HBsAb test result changes from HBsAb negative or missing at baseline to HBsAb positive at a postbaseline visit.
- HBeAg seroconversion is defined as HBeAg loss and HBeAb test result changes from HBeAb negative or missing at baseline to HBeAb positive at a postbaseline visit.
- ALT normalization is defined as ALT > ULN (by central laboratory normal range or 2018 AASLD normal range) at baseline but within normal range at a postbaseline visit.

Both baseline and postbaseline borderline serology results will be imputed using the following rules:

- HBsAg and HBeAg borderline will be considered as HBsAg positive and HBeAg positive.
- HBsAb and HBeAb borderline will be considered as HBsAb negative and HBeAb negative.

For the above definitions, baseline will be replaced with open-label baseline for the analyses of subjects in the Open-Label FAS, and with TFFU baseline for the analyses of subjects in the TFFU FAS.

6.2.2. Analysis Methods for Secondary Efficacy Endpoints

The primary analysis of the proportion of subjects in the Full Analysis Set with HBV DNA ≥ 20 IU/mL (as determined by the modified US FDA-defined snapshot algorithm {U. S. Department of Health and Human Services 2015}) will be repeated for the Week 96 endpoint using the FAS. The Week 96 analysis window is defined as from Study Day 589 to Study Day 840, inclusive.

The analyses for the other secondary efficacy endpoints will be conducted using the FAS. All secondary efficacy endpoints involving proportions will be analyzed from baseline to Week 96 using both the Missing Failure (M F) approach and the Missing Excluded (M E) approach, unless otherwise specified. In the M E approach, all missing data will be excluded in the computation, and in the M F approach, all missing data will be treated as failures and included in both the numerator and denominator. P-values will be calculated using the CMH test stratified by baseline HBeAg status (HBeAg-positive or HBeAg-negative) and age (< 50 or ≥ 50 years), and the proportion difference between the 2 treatment groups and the associated 95% CIs will be calculated based on the stratum-adjusted MH proportion.

The change from baseline in \log_{10} (HBsAg) (IU/mL), both overall and by baseline HBeAg status, and ALT will be summarized by visit using observed data (ie, missing data will be excluded). The p-value, differences in change from baseline in \log_{10} (HBsAg) (IU/mL) and ALT between the 2 treatment groups and the associated 95% CI will be constructed using analysis of variance (ANOVA) models, including treatment group, baseline HBeAg status (HBeAg-positive or HBeAg-negative), and age (< 50 or \geq 50 years) as fixed effects in the model. For the analysis of change from baseline in \log_{10} (HBsAg) (IU/mL) by baseline HBeAg status, only treatment group and age (< 50 or \geq 50 years) will be included as fixed effects in the model.

In addition, the proportion of subjects in the FAS with HBV DNA < 20 IU/mL, the proportion of subjects with normal ALT by the central laboratory and 2018 AASLD criteria (ULN is 35 U/L for males and 25 U/L for females) using the M E approach, and the mean change from baseline in log10 (HBsAg) (IU/mL) and ALT (U/L) will be plotted with 95% CI over time using observed data from baseline to Week 96.

FibroTest score will be summarized using descriptive statistics (sample size, mean, SD, median, Q1, Q3, minimum, and maximum) by treatment group for subjects in the FAS. The p-value, differences in change from baseline in FibroTest score between the 2 treatment groups and the associated 95% CI will be constructed using ANOVA models, including treatment group, baseline HBeAg status (HBeAg-positive or HBeAg-negative) and age (< 50 or ≥ 50 years) as fixed effects in the model. A shift table of fibrosis stage from baseline based on the FibroTest score at Week 24, 48, and 96 will be provided. Mean change from baseline in FibroTest score will be plotted with 95% CI over time using observed data from baseline to Week 96. A listing of fibrosis assessment by FibroTest will also be provided.

All the analyses of the secondary efficacy endpoints, using both the M F and the M E approach, and plots described above will be repeated for subjects in the Open-Label FAS from open-label baseline to Week 96. No statistical comparisons will be performed.

For subjects in the TFFU FAS, only HBV DNA, ALT, HBsAg, HBeAg loss/seroconversion, and HBsAg loss/seroconversion endpoints will be summarized by visit in the TFFU phase as described above only using the M E approach. No statistical comparisons will be performed.

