2. OBJECTIVES

The primary objectives of this study are as follows:

- To evaluate the efficacy of switching to TAF 25 mg QD versus continued TDF 300 mg QD in virologically suppressed subjects with chronic HBV as determined by the proportion of subjects with HBV DNA ≥ 20 IU/mL (as defined by the modified US FDA-defined snapshot algorithm) at Week 48
- To compare the safety and tolerability of switching to TAF 25 mg QD versus continuing TDF 300 mg QD in virologically suppressed subjects with chronic HBV at Week 48

The key secondary objectives of this study are as follows:

- To compare the safety of switching to TAF 25 mg QD versus continued TDF 300 mg QD as determined by the percent change from baseline in hip and spine BMD at Week 48
- To compare the safety of switching to TAF 25 mg QD versus continued TDF 300 mg QD as determined by the change from baseline in estimated creatinine clearance by Cockcroft-Gault method (eGFR_{CG}) at Week 48

Other secondary objectives of this study are as follows:

- To evaluate the proportion of subjects with HBV DNA < 20 IU/mL and target detected/not detected (i.e. < LLOD) at Week 48 in subjects switched to TAF 25 mg QD versus continued TDF 300 mg QD
- To compare the safety of switching to TAF 25 mg QD versus continued TDF 300 mg QD for 48 weeks followed by open-label TAF for 48 weeks as determined by the percent change from baseline in hip and spine bone mineral density (BMD) at Week 96
- To compare the safety of switching to TAF 25 mg QD versus continued TDF 300 mg QD as determined by the change from baseline in estimated creatinine clearance by Cockcroft-Gault method (eGFR_{CG}) at Week 96
- To compare the serological response (loss of HBsAg and seroconversion to anti-HBs, and loss of HBeAg and seroconversion to anti-HBe in HBeAg-positive subjects) of switching to TAF 25 mg QD versus continued TDF 300 mg QD at Week 48
- To compare biochemical response (normal ALT and normalized ALT) of switching to TAF 25 mg QD versus continued TDF 300 mg QD at Week 48

- To compare the change in fibrosis as assessed by FibroTest[®] after switching to TAF 25 mg QD versus continued TDF 300 mg QD at Weeks 48
- To evaluate the comparative open-label efficacy and safety of switching to TAF 25 mg QD from Week 48 through Week 96 in subjects initially randomized to TAF 25 mg QD and in subjects sequentially treated with continued TDF 300 mg QD for 48 weeks and then switched to open-label TAF 25 mg QD

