5. INVESTIGATIONAL MEDICINAL PRODUCTS

5.1. Randomization, Blinding and Treatment Codes

A centralized randomization procedure via an Interactive Voice/Web Response System (IVRS/IWRS) will be used for this study, whereby study treatment will be assigned to subjects according to the randomization schedule. A unique subject number will be provided during randomization. Eligible subjects (n = 300) will be randomized 1:1 to receive either blinded TAF 25 mg and TDF matched placebo (n = 150) or TDF 300 mg and TAF matched placebo (n = 150) for 48 weeks. Subjects will be stratified by HBeAg status (HBeAg-negative [and anti-HBe positive] vs. HBeAg-positive) and age (> 50 years vs. < 50 years). At Week 48, all subjects will be switched to open-label TAF 25 mg QD for an additional 48 weeks (through Week 96/ED). For the entire duration of the study, subjects and investigators will remain blinded to the initial treatment regimen to which the subjects were randomized.

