8.6. Efficacy Analysis

8.6.1. Primary Analysis

The primary analysis will be performed when the last subject has completed Week 48 assessments or discontinued prematurely. The primary analysis will consist of a non-inferiority evaluation of efficacy of TAF versus TDF, with respect to the proportion of subjects with HBV DNA \geq 20 IU/mL at Week 48 (as defined by the modified FDA snapshot Algorithm). It will be concluded that TAF is not inferior to the TDF if the upper bound of the two-sided 95% confidence interval of the difference between treatment arms (TAF arm – TDF arm) in the response rate is less than 4% (i.e., a margin of 4% is applied to non-inferiority assessment). The 95% confidence interval will be constructed using the normal approximation method based on stratified Mantel-Haenszel proportions, where stratification factors are HBeAg status (HBeAg positive or negative) and age (\geq 50 or < 50 years).

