8.9. Sample Size

With respect to the primary efficacy endpoint of proportion of suppressed subjects with HBV DNA \geq 20 IU/mL (current assay LLOQ), as determined by the modified US FDA-defined snapshot algorithm, at Week 48, when the sample sizes are 230 (TAF 25 mg arm) and 230 (TDF 300 mg arm), a two-group, large-sample normal approximation test of proportions with a one-sided 0.025 significance level will have 80% power to establish non-inferiority of TAF to TDF. It is assumed that both treatment arms will have subjects who have HBV DNA \geq 20 IU/mL (as defined by the modified US FDA-defined snapshot algorithm) at a rate of 2.4% at Week 48 (based on the rates of suppressed subjects having HBV DNA \geq 29 IU/mL [the LLOQ of assay during those studies] after 48 weeks of treatment from the combined data of studies GS-US-174-0102 and GS-US-174-0103 with the ratio of HBeAg- to HBeAg+ subjects assumed to be 2:1), with a non-inferiority margin of 4%.

The proposed sample size (n = 230 for the TAF 25 mg arm, n = 230 for the TDF 300 mg arm) also provides > 99% power to detect a 1.81% difference in the percentage change from baseline in hip BMD at Week 48 (assuming a 1.47% [SD 2.71%] change from baseline in TAF 25 mg arm and -0.34% [SD 2.83%] change from baseline in the TDF 300 mg arm, with a two-sided $\alpha = 0.05$); a > 99% power to detect a 2.00% difference in the percentage change from baseline in spine BMD at Week 48 (assuming a 1.56% [SD 3.84%] change from baseline in the TAF 25 mg arm and -0.44% [SD 4.14%] change in the TDF 300 mg arm, with a two-sided $\alpha = 0.05$); a 97% power to detect a 4.9 mL/min difference in the change from baseline in eGFR_{CG} at Week 48 (assuming a 1.3 mL/min [SD 13.2] change from baseline in the TAF 25 mg arm and -3.6 mL/min [SD 13.0] change from baseline in the TDF 300 mg arm, with a two-sided $\alpha = 0.05$). These assumptions were derived from an HIV switch study (GS-US-292-0109) due to the unavailability of switch data from TAF HBV studies.

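### SAP 6.2.2 repeats the TAF-versus-TDF non-inferiority analysis at Week 96, when the contrast is immediate versus delayed switch to TAF, so the 4% margin should not be applied there

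*SAP*

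**What the plan says.** SAP 6.2.2 states that the primary analysis of the proportion with HBV DNA ≥ 20 IU/mL by the modified snapshot algorithm "will be repeated for the Week 96 endpoint using the FAS", with a window of Study Day 589 to 840. SAP 6 confirms that this is inferential: FAS data are summarised "from baseline up to Week 96 and statistical comparisons will be performed". SAP 3.1.5 groups the FAS by the arm assigned at randomisation.

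The analysis being repeated is defined in Protocol 8.6.1: "The primary analysis will consist of a non-inferiority evaluation of efficacy of TAF versus TDF". TAF is declared non-inferior if the upper limit of the two-sided 95% CI for TAF minus TDF is below 4%. SAP 6.2.2 does not restate the margin for Week 96, nor does it leave any part of the primary analysis out of the repeat.

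Protocol 5.1 describes what happens in between: "At Week 48, all subjects will be switched to open-label TAF 25 mg QD for an additional 48 weeks". Protocol 3.1 and SAP 1.2.4 limit entry to subjects who complete 48 weeks.

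**The concern.** A non-inferiority margin belongs to a particular contrast. Here it was set for TAF against continued TDF, and after Week 48 no continuing subject takes TDF. If both arms receive the same drug, their rates tend to converge whatever the true TAF-TDF difference is. The Week 96 interval can then fall below 4% because of the switch, not because TAF matches TDF. Read literally, the plan would place a TAF-versus-TDF non-inferiority result in the Week 96 tables, and that could be cited as 96-week comparative evidence. The SAP offers no Week 96 hypothesis, no reason for keeping the margin, and no caution on interpretation.

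**Working it through.** **Inputs.** From Protocol 8.9: 230 per arm, a common rate of 2.4%, a 4% margin, one-sided 0.025 and 80% power. The Week 96 window is in SAP 6.2.2 and the nominal Week 48 day (336) is in SAP Table 3-1. TAF rates above 2.4% are my assumptions for illustration. All calculations are unstratified, whereas the plan uses stratified Mantel-Haenszel proportions.

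**Timing.** 589 − 336 = 253 days, about 36 weeks. Even the first day of the Week 96 window falls roughly 36 weeks after the nominal switch.

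**Step 1: reproduce the stated power.** With p_T and p_C the proportions with HBV DNA ≥ 20 IU/mL in the TAF and comparator arms:

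SE = √[p_T(1−p_T)/230 + p_C(1−p_C)/230]; chance of meeting the margin = Φ[(0.04 − (p_T − p_C))/SE − 1.96].

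At 2.4% in both arms, SE = √(2 × 0.024 × 0.976/230) = 0.01427, and Φ(0.04/0.01427 − 1.96) = Φ(0.843) = 80.0%. This matches the stated 80%. Exact binomial enumeration of the same interval rule gives 79.0%.

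**Step 2: TAF worse by exactly the margin, concurrent TDF (6.4% versus 2.4%).** The numerator is 0.04 − 0.04 = 0, so the chance is Φ(−1.96) = 2.5% (exact 3.2%).

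**Step 3: the same TAF rate after the switch (6.4% in both arms).** SE = √(2 × 0.064 × 0.936/230) = 0.02282. The chance is Φ(0.04/0.02282 − 1.96) = Φ(−0.207) = 41.8% (exact 42.0%).

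**Step 4: other assumed rates (exact enumeration).**

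| TAF vs TDF rate | Concurrent TDF | Both arms at TAF rate |
|---|---|---|
| 6.4% vs 2.4% | 3.2% | 42.0% |
| 7.4% vs 2.4% | 1.0% | 37.6% |
| 5% vs 1% | 4.1% | 50.8% |

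With both arms on TAF, the result follows the common event rate: by the formula, 99% at 1.0%, 80% at 2.4%, 59% at 4.0% and 42% at 6.4%. The TAF-TDF difference enters only through that common rate.

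**Step 5: incomplete convergence.** Suppose a fraction f of the 4-point gap remains, so that p_C = 6.4% − f × 4%. The formula gives:

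| f | Chance of meeting the margin |
|---|---|
| 0 | 41.8% |
| 5% | 38.9% |
| 10% | 36.0% |
| 25% | 27.6% |
| 50% | 15.6% |
| 100% | 2.5% |

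The 5% row corresponds to 5% of the TDF arm never switching and keeping the full TDF advantage. That share is an assumption, borrowed from the 4.9% who discontinued blinded drug in the two earlier Phase 3 studies (Protocol 1.2.3).

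**The case against.** Several points on the other side are sound.

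- **No Week 96 claim is written.** A reader might infer that the SAP plans a formal pass/fail non-inferiority test at Week 96. SAP 6.2.2 names no hypothesis, margin or decision rule for that time. Repeating the analysis could mean only the snapshot classification and the stratified difference with its CI. SAP 6.1.1 refers details to a separate Week 48 SAP that is not among the documents. The margin comes in through Protocol 8.6.1, so this is an ambiguity that the literal text resolves the wrong way.
- **Week 96 is already of lower standing.** Protocol 8.4 controls type I error only for Week 48 endpoints. Protocol 8.6.2 allows exploratory Mantel-Haenszel tests for categorical secondary endpoints. The Week 96 bone and renal objectives and the open-label objective in SAP 1.1 already describe TAF against TDF followed by TAF. SAP 6.2.2 makes no statistical comparison in the Open-Label FAS. The switch is fully disclosed.
- **The 42% does not measure maintained non-inferiority.** A reader might take it as the chance of passing at Week 48 and again at Week 96. That joint chance cannot exceed the Week 48 chance, about 3% in the same scenario.
- **The contrast is diluted, not empty.** It would go too far to say that the entire TDF arm switches or that the comparison cannot show TAF to be worse. Subjects who stop before switching stay in the FAS under their randomised arm. Under the snapshot rules, those who stop for lack of efficacy, or with a last on-treatment value ≥ 20 IU/mL, still count as events.

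These points limit the size of the problem. They do not give the 4% margin a meaning at Week 96.

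**Conclusion.** The point holds as one of inference and labelling on a secondary endpoint. Followed as written, SAP 6.2.2 carries a TAF-versus-TDF non-inferiority analysis to a time when continuing subjects in both arms take TAF. The FAS contrast there is immediate versus delayed switch, and meeting 4% is weak evidence on TAF against continued TDF.

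The illustration of about 3% rising to about 42% rests on assumed rates, an unstratified interval and full convergence of the switched arm. It falls to 15.6% if half the gap persists.

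Nothing here supports doubt about the Week 48 primary result, which is a concurrent comparison and was analysed separately. Protocol Section 2 also words the Week 96 renal objective as TAF "versus continued TDF 300 mg QD as determined by the change from baseline in estimated creatinine clearance by Cockcroft-Gault method (eGFR_{CG}) at Week 96", although continuing subjects no longer take TDF by then. The synopsis, Protocol 8.1.1 and SAP 1.1 describe TDF followed by TAF. That is a separate drafting slip in a safety objective with no margin attached, and it adds no weight to this point.

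**What to change.** In SAP 6.2.2, replace the sentence that repeats the primary analysis with text to this effect: the Week 96 proportion with HBV DNA ≥ 20 IU/mL will be reported by randomised sequence (TAF for 96 weeks; TDF for 48 weeks then TAF for 48 weeks). The stratum-adjusted difference and its 95% CI will be labelled as immediate versus delayed switch. The 4% margin will not be applied, and no TAF-versus-TDF non-inferiority conclusion will be drawn. Table titles should follow.

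The available copy is marked final v1.0. If it stands as final, record the change in the CSR, as SAP 1 provides. Separately, align the Week 96 eGFR objective in Protocol Section 2 with Section 8.1.1.

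The cost is a few lines of wording, with no change to data collection, sample size or trial conduct. The sponsor gives up a Week 96 non-inferiority statement.
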